## 8.5. Cerebral physiology assessments

Cerebral physiology assessment acquisition will be specified in the cerebral physiology assessment study manual.

- **TMS task:** We will measure the cortical silent period from the right first dorsal interosseous (FDI), participants will maintain tonic muscle activation of the right FDI at 10% maximal voluntary contraction for 5 s per trial, while TMS is delivered to the left M1 at the intensity that evoked a 1 mV MEP in right FDI at rest for 15 trials.
- **Cerebrovascular responsiveness testing** TCD: Blood velocity through the left and right middle (MCAv) cerebral artery will be measured, as a proxy of blood flow, using TCD ultrasound. 2MHz TCD probes will be used to insonate the artery via the temporal window by a trained ultrasound sonographer and fixed in place for the duration of the battery using

an adjustable headset. These measures will be collected continuously throughout the battery to track changes across all rest periods and tasks.

- fNIRS+EEG: Cortical haemodynamics and the underlying neural activity will be assessed simultaneously during a cognitive challenge task using a commercially available combined fNIRS and EEG system to identify detectable multivariate features. In addition, a resting state EEG assessment will be collected to assess if any changes in the ongoing oscillatory activity. In particular, we will focus on EEG slowing, which manifests as an increase in delta and theta frequency power and decrease in alpha frequency power.
- **NVC:** Neurovascular function within specific regions of the frontal cortex in response to Attention Network and choice reaction time tasks will be assessed using the combined fNIRS and EEG system.
- **CVR:** CVR is assessed by the continuous measurement and calculation of MCAv differences in response to changes in circulating carbon dioxide, induced through the inhalation of a gas mixture containing elevated CO2 levels and via hyperventilation of ambient room air. The protocol for exposure to CO2 will consist of 4-minutes of continuous inhalation of a mixture containing 5% CO2 in air, as per the guidelines [51, 52] to ensure a steady-state response in MCAv vasodilatory responses. Following the 4-min CO2 inhalation procedure, participants will complete guided mild hyperventilation for 2 minutes to reduce end-tidal CO2 by 10 mmHg. The 4-min CO2 inhalation part of the protocol will also be part of the cerebral physiology MRI session (see below). In addition, the same CVR protocol will be carried out with fNIRS and EEG.
- **CA:** This task will assess CA via the relationship between changes in MCAv induced by transient and spontaneous alterations in beat-by-beat blood pressure. CA will be assessed by transfer function analysis of MCAv over repeated lower limb activity (e.g. cycles of squat-to-stand / leg flexion-extension) at a frequency of 0.10 Hz, which have been shown to provide reliable and robust measures of coherence (correlation index), phase (timing buffer) and gain (amplitude buffer) [54].
- Exercise task: In this task, participants will complete 3 maximal voluntary contractions, followed by a 5-minute maximal endurance rhythmic hand grip exercise task (contraction every second, with the aim to generate maximal cumulative force over the 5-minute period) using a hand grip dynamometer [221]. Throughout the task, fNIRS and EEG measures will be obtained to determine changes in cerebral haemodynamics, alongside ratings of perceived physical exertion and fatigue [221].

## 8.6. Imaging assessments

Participants will undergo MEG, MRI and fMRI scans.

• **MEG:** Participants will undergo a MEG scan and undertake the following tasks:

**Resting-state data:** This task allows for identifying the resting-state networks. In the fMRI data this will be reflected in the correlation structure of the BOLD signal in different regions. In the MEG data the network dynamics will be reflected in how oscillatory activity interacts between different regions in the delta, alpha and beta band.

**Spatial attention task:** This task probes the neuronal activity associated with the allocation of spatial attention. The allocation of attention will be reflected in the modulation of alpha and gamma activity in posterior regions and their interaction with the dorsal attention

network exercising the top-down control. The BOLD-fMRI signal will likewise be modulated in posterior visual regions as well as in the dorsal attention network.

**CRT task:** This is a simple sustained attention task that taps into processing speed deficits. In fMRI, the CRT captures the engagement of bilateral sensory, motor, and superior parietal regions, as well as the thalami (amongst others).

**Implicit face processing task:** Participants will complete an implicit face processing task in which emotional stimuli are comprised of happy, angry, neutral faces.

- **MRI:** Participants will undergo 3T MRI scans, including structural (T1, FLAIR, DTI) and functional MRI (resting state, CRT task as described above)
- MRI physiology: This scan will include baseline perfusion and cerebrovascular reactivity measures. These will be used to provide complementary measures of CBF and CVR to those which are acquired with Doppler and NIRS. These measures will interrogate the macro- and micro-vasculature with regional specificity using arterial spin labelling, Phase contrast angiograph (PCA) and BOLD-CVR.

## 8.6.1. Exploratory Imaging assessments

Participants will undergo OPM-MEG and 7T MRI scans at the University of Nottingham:

- **OPM-MEG:** same tasks as above for standard MEG, exploring the potential for increased signal to noise and reduced movement artefacts during data acquisition using OPM-MEG.
- **7T MRI:** scan sequences to be performed: multi-echo gradient echo from which SWI, QSM and T2\* maps will be derived, T1 weighted anatomical, T2 weighted anatomical, Angiography, 4D Phase contrast angiography (measures blood flow through vascular tree), and Magnetisation Transfer sequence (investigate markers of neuroinflammation).

## 8.7. Withdrawal and changes in levels of participation

Informed consent is defined as the process of learning the key facts about a clinical study before deciding whether or not to participate. It is a continuous and dynamic process and participants should be asked about their ongoing willingness to continue participation at all visits. Participants should be aware from the beginning that they can freely withdraw (cease to participate) from the study at any time. A participant may wish to cease to participate in a *particular* aspect of the study.

Participants found to be ineligible post-registration should be followed up according to all study processes and will still have their data analysed unless they explicitly change their level of participation.

The changes in levels of participation within the study are categorised in the following ways:

**No in-person assessment:** The participant would no longer like to attend in person follow-up but is willing to be followed up remotely in accordance with the schedule of assessments and if applicable using any central UK NHS bodies for long-term outcomes (i.e., the participant has agreed that data can be collected and used in the study analysis).

**No study related follow-up:** The participant does not wish to take further part in study-specific follow-up but is willing to be followed up at standard clinic visits and if applicable using any central UK NHS bodies for long-term outcomes (i.e., the participant has agreed that data can be collected at standard clinic visits and used in the study analysis, including data collected as part of long-term outcomes).

No further data collection: The participant is not willing to be followed up in any way for the

purposes of the study AND does not wish for any further data to be collected (i.e. only data collected prior to any changes of levels in participation can be used in the study analysis).

The details of changes of levels in participation within the study (date, reason and category of status change) should be clearly documented in the source documents and will be recorded on the study database using a Change of Status form.

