#### 1.2.2. Justification for design

- Why prospective cohort study? A prospective cohort design allows us to observe the development and resolution of symptoms in real-time. By including all new injuries where possible, we will minimise selection bias and symptom recall error.
  - We exclude previous head injuries with ongoing sequelae as this would make the cohort too heterogeneous and risk failure to identify useful biomarkers.
  - $\circ$   $\;$  We exclude patients with a prior diagnosis of PTSD to allow us to identify biomarkers

which increase the likelihood of developing PTSD following mTBI.

- Why variability study? Understanding the variability of biomarkers is critical to later using them in a predictive model; this study will allow us to collect this vital data.
- Why case-control cohort study? Identifying new biomarkers in someone with mTBI and a healthy control will allow us to track changes in these biomarkers over the course of recovery. We should get a reliable measure of 'normal' variability in outcomes across the course of the study.

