# 1.13. Rationale for candidate biological variability study (nested study1)

The vestibular, visual, brain imaging, fluid biomarkers and cerebral physiology workstreams will all be involved in the variability study. This is due to the need to estimate the reliability of the techniques used and allow for this in subsequent use of measurements and interpretation of results. Many measures have not been validated. We will validate the techniques used to establish the variation between participants and the variation within participants. It is important for biomarkers to be reproducible. This will inform the main study, as biomarkers that are not fit for purpose due to excess variability may be dropped from further analyses, as we would suggest the need for refinement of these measurements.

Headache, mental health and the cognition workstreams are not included in the variability study. Headache is assessed utilising clinical history to assign phenotype, diaries to describe a patient's experience of their symptoms and patient reported outcome measures (such as the Headache Impact Test-6, or HIT-6) to describe disability. These are already validated tools (HIT-6) and hence variability does not need assessing [211]. The questionnaires involved in the mental health workstream have also been validated [212-218]. Cognitive outcomes will not be looked at due to test-retest reliability having already been determined by the Department of Brain Sciences at Imperial College London (unpublished data) for the cognitive tests proposed.

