#### 4.2.2. Exclusion

- Prior diagnosis of PTSD or severe mental illness (as defined by Section 23.4 Appendix 2)
- Pregnancy
- Prior brain injury (from trauma, stroke or other aetiologies) without full functional and symptomatic recovery
- Inability to comply with study schedule or follow-up
- Inability to provide informed consent (e.g. due to cognitive impairment)
- Inability to safely enter the MRI environment (for imaging variability and case-control study)
- Any progressive neurodegenerative or neuroinflammatory condition
- Cardiovascular or cerebrovascular disease or hypertension (no current diagnosis/medication)
- Alcohol use disorder or drug dependence, in the medical opinion of the investigator
- Patients with medical conditions that are unstable or untreated
- History of pituitary hormone deficits

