## 4.3. Nested study 2: Observational case-control prospective study

mTBI cohort as per main study in Section 4.1. Healthy controls as per biological variability study in Section 4.2.

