### 14.4. Development of a prognostic model

We aim to develop multivariable statistical models that can predict sequelae of mTBI using the investigated biomarkers. The sequelae of mTBI being examined are headache, vestibular dysfunction, mental health (depression, PTSD), cognition, global function and full return to work, play or duty. These clinical outcomes are measured via mean monthly headache days, vestibular disturbance questionnaire, self-reported PHQ-9, self-reported PCL-5, corrected global composite score, and MPAI, respectively. Global composite score and MPAI are continuous outcomes; monthly headache days is a count outcome; and clinical thresholds to PHQ-9 and PCL5 will categorise patients into those with and without depression and PTSD respectively (binary outcomes). Each of these outcomes will be measured at 6-, 12- and 24-months post-injury.

Whilst absolute values of biomarkers will be valuable all biomarkers are measured on multiple occasions, as such characteristics such as the rate of change of biomarkers and time until normalisation will also be considered as potentially important data in their own right.

We aim to recruit 610 participants to follow-up for the prognostic modelling phase of the project. At 6 months, for each of the headache, depression and PTSD outcomes, we will have sufficient sample size to investigate a model with 10 candidate parameters; for the global composite score and MPAI outcomes, we will have sufficient sample size to investigate a model with 44 parameters. Sample size calculations were based on methods proposed by Riley [222, 223]. This will allow for 10% drop out which will be reviewed, and the analysis plan modified accordingly.

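### Section 8.7 keeps participants found ineligible after registration in every analysis, with no exception for prior PTSD in the PTSD model or for controls who fail the healthy-control criteria (minor, cheap to fix)

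*Protocol*

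**What the plan says.** Section 8.7 sets a rule for late-discovered ineligibility: "Participants found to be ineligible post-registration should be followed up according to all study processes and will still have their data analysed". The single exception lies in the participant's hands, since the rule applies "unless they explicitly change their level of participation". Three reduced levels of participation follow, and each is worded as the participant's wish; the first begins "The participant would no longer like to attend in person follow-up". Even the strongest level, which stops all further collection, leaves earlier data available for analysis. The rule does not vary by criterion or by cohort.

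Other sections give two groups of criteria a scientific purpose.

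- **PTSD.** Section 1.2.2 says "We exclude patients with a prior diagnosis of PTSD to allow us to identify biomarkers" that raise the likelihood of PTSD after mTBI. Section 14.4 then defines the outcome: "clinical thresholds to PHQ-9 and PCL5 will categorise patients into those with and without depression and PTSD respectively". It sets no condition about PTSD before the injury. PTSD is a named secondary outcome in Section 9.1.
- **Healthy controls.** Section 4.2.2 defines them by exclusions, among them "Cardiovascular or cerebrovascular disease or hypertension" and past pituitary hormone deficits. Section 4.3 carries these over: "Healthy controls as per biological variability study in Section 4.2".

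Both nested studies feed biomarker selection. Section 1.13 says "biomarkers that are not fit for purpose due to excess variability may be dropped from further analyses", and Section 14.3 makes the variability and case-control results available to the Delphi panel.

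**The concern.** Retaining everyone after a late eligibility finding is a habit from randomised trials, where it protects the randomised comparison. Nothing is randomised here. In the case-control study, membership of the healthy group rests on the criteria themselves, so keeping people who fail them protects no comparison and blurs the reference group. In the PTSD model, a retained patient with a prior diagnosis can supply an event of the kind the exclusion was written to keep out.

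Late discovery is foreseeable. Visit 1 collects only the basic data needed to enrol (Section 7.5.1), the structured medical and psychiatric history is due before the first clinical visit (Section 8.2.1), and Table 4 places the primary care records check at visits 3 and 8, after registration.

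At stake are the meaning of one secondary outcome and the cleanliness of the reference data shown to the Delphi panel. On procedures, the stake is a smaller one: 8.7 gives the investigator no written route to pause a test when the failed criterion bears on safety.

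**Working it through.** The point is mainly textual. The arithmetic only gauges how much it could matter. The protocol states no ineligibility rate, so every rate and offset below is an assumption.

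**1. Share of each control group.** One retained ineligible control is 1/100 = 1% of the case-control arm (Section 14.2) and 1/20 = 5% of a variability control cohort (Section 14.1).

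**2. Variability study.** Section 14.1's example SDs are 0.5 (analytical), 1.0 (within-individual) and 2.3 (between-individual).

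- Plan's own figure: ICC = 2.3² / (2.3² + 1.0² + 0.5²) = 5.29 / 6.54 = 0.809. This matches the plan's approximate 80%, with its interval of 65% to 89%.
- If one of 20 controls is offset by d between-individual SDs, the expected between-individual variance becomes 5.29 × (1 + d²/20). The other two components do not change.

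| Assumed d | Variance | Between-individual SD | ICC |
|---|---|---|---|
| 0 | 5.29 | 2.30 | 0.809 |
| 1 | 5.55 | 2.36 | 0.816 |
| 2 | 6.35 | 2.52 | 0.835 |
| 3 | 7.67 | 2.77 | 0.860 |

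The biomarker looks slightly more reliable than it is, but every value stays inside the plan's interval. The within-individual SD is untouched.

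**3. Case-control study.** Section 14.2's continuous example has a difference of 1.5, SD 3 and 100 per group. The significance level is not stated; a two-sided 5% t-test is assumed.

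- Plan's own figure: power is 94.0%, consistent with the stated more than 90%.
- If a share f of controls has fully case-like values, the difference becomes 1.5 × (1 − f). At f = 2% it is 1.470 and power is 93.2%. At f = 5% it is 1.425 and power is 91.7%.
- Leaving those controls out instead gives 93.8% (100 v 98) or 93.5% (100 v 95). Exclusion therefore recovers 93.8 − 93.2 = 0.6 points, or 93.5 − 91.7 = 1.8 points.

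**4. PTSD model.** 610 less 10% drop-out = 549 (Section 14.4). Let p be the rate of new PTSD, f the share retained despite a prior diagnosis, and q the chance that such a person scores above threshold. The share of events that come from people with prior PTSD is f·q / [(1 − f)·p + f·q].

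- Low end: p = 20%, f = 1%, q = 50% gives 0.005 / (0.198 + 0.005) = 2.5%.
- At f = 1%, p = 10%, q = 80%: 0.008 / (0.099 + 0.008) = 7.5%.
- Extreme end: p = 10%, f = 5%, q = 80% gives 0.040 / (0.095 + 0.040) = 29.6%.

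The last figure needs all three assumptions to be unfavourable together. Eligibility is confirmed before registration (Section 6.2), which argues for a small f. These are shares of events, not estimates of bias in the model.

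**The case against.** The best case for leaving the text alone has four parts.

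- **The analysis sets belong in the SAP.** Section 8.7 sits among withdrawal rules and names no analysis set; a SAP might exclude people from one main model and still analyse their data in a sensitivity analysis. This has some force, but it strains the plain wording, which keeps their data in the analysis and lets only the participant opt out. A SAP author reading 8.7 would not find permission to exclude.
- **Retained prior PTSD is not necessarily a false event.** A reader might infer that prior PTSD defines the outcome, or that every such event is old illness. The protocol does not support that. The PCL-5 threshold defines the outcome, and a remitted patient who crosses it at 6 months may have had a real recurrence after injury. Past psychiatric history, PCL-5 and the MINI are also recorded (Section 8.2.1), so the modeller can see who these people are. This stands; the conflict is with the stated reason for the exclusion.
- **Safety is largely covered.** A reader might infer that 8.7 forces sites to perform unsafe tests. It does not support that reading. Eligibility is confirmed before registration, MRI has its own screening with imaging omitted on failure (Section 4.1.2), participants may decline part of the study (Section 8.7), and Section 16 keeps clinicians' duty to act. No section ties pregnancy or unstable illness to a particular test. Only a missing sentence on investigator discretion remains.
- **Exclusion has its own bias.** Who is found ineligible depends partly on how it is detected. This also stands, and is why the fix needs the all-inclusive sensitivity analysis.

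**Conclusion.** The point holds as a minor one. Section 8.7 is a stated rule rather than an omission, and for two groups it works against the protocol's own purposes: patients with prior PTSD in the PTSD-outcome model, and controls who fail 4.2.2 in the two nested comparisons.

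The likely effect is small. Under the assumed offsets and rates, the ICC stays between 0.81 and 0.86 and case-control power stays above 91%. The PTSD share could be larger, but only under stacked assumptions that the protocol neither supports nor rules out. The route to biomarker selection is indirect, because the Delphi panel judges prognostic capability and uses the nested results only as needed.

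A reader might infer that the main prognostic result is compromised. It is not: return to play, work or duty is little affected. Following up ineligible participants is also reasonable in itself and should continue.

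**What to change.** Amend Section 8.7 so that follow-up and all other analyses stay as written, with these additions:

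1. Participants with a prior PTSD diagnosis are left out of the main PTSD-outcome model only.
2. Controls who fail Section 4.2.2 are left out of the main case-control and variability analyses.
3. A sensitivity analysis for each of these includes everyone.
4. The investigator may withhold an in-person procedure, with a documented reason, when the failed criterion bears on safety.

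The cost is a few sentences and slightly smaller analysis sets. At an assumed 1% to 3% with prior PTSD, 549 × 0.01 = 5.5 to 549 × 0.03 = 16.5 patients would leave the PTSD model, and each excluded control costs 1% or 5% of its group. Exclusion will depend partly on how ineligibility comes to light; the sensitivity analysis shows whether that matters. No new data collection is needed.

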# 9. OUTCOME MEASURES

## 9.1. Main study outcomes

- Primary outcome: Ability of candidate biomarkers to predict full return to play, work or duty at 6 months post-injury.
- Secondary outcomes: Ability of candidate biomarkers to predict global function, persistent PTH, cognitive dysfunction, depression, PTSD, vestibular disturbances and physical function at 6 months post-injury and beyond.
- Exploratory outcomes: Accuracy of a multifaceted computer modelled biomarker algorithm to predict sequelae of mTBI (full return to play, work or duty, persistent PTH, cognitive dysfunction, depression, PTSD, vestibular disturbances, and physical function).

## 9.2. Biological variability study outcomes

The primary outcome is the variability of candidate biomarkers for each workstream.

The secondary outcome is the variability of candidate brain imaging biomarkers between imaging centres (University of Birmingham, Aston University and University of Nottingham). For reasons of capacity as well as real world applicability, scanning in the main study will be split across the different imaging centres.

## 9.3. Case-control outcomes

The primary outcome is identification of novel candidate biomarkers.

The exploratory outcome is to gain mechanistic insights into the candidate biomarkers.

